10.5 Subject Diary and Patient Reported Outcomes

10.5.1 Subject Diary

An electronic subject diary will be provided to each subject at the screening visit to record the following information:

1. Infusion record for BAX 855
2. Details of bleeding episodes and response to treatment
3. Untoward events
4. Concomitant medications (including immunizations) and non-drug therapies
5. Patient Reported Outcomes (PROs)

For each bleeding episode, the following information will be recorded by the subject/subject's caregiver or by authorized, qualified personnel at the study site:

- Location of bleed, eg, joint, soft tissue, muscle, body cavity, intracranial, other.
- Type of bleed, ie, spontaneous (definitely no injury/trauma), injury (definitely due to injury/trauma), or unknown (pediatric subject was not observed by an adult to reliably determine and verify whether it was spontaneous or injury-related).
- Severity of bleed, eg, minor, moderate, major (see [Table 3](#)).
- Date and time of onset of bleed.
- Date and time of each infusion of BAX 855 required to achieve adequate hemostasis.
- Date and time of resolution of bleeding episode.
- Overall clinical efficacy rating according to the rating scale as described in [Table 4](#) at 24 (± 2) hours after initiation of treatment and at resolution of bleed.

Details pertaining to all treatments for each bleed, including response to treatment, will be recorded by study subjects/subjects' caregiver in subject diaries provided by the sponsor or sponsor's representative.

AEs and the details of concomitant medication used coincident with the treatment of all acute bleeding episodes will be recorded.

NOTE: Bleeding episodes are not to be reported as AEs (Section [12.3](#)).

Subjects and/or their legally authorized representatives will be trained on use of the diary. The diary will be provided in electronic format and remain with the subject for the duration of the study. The investigator will review the diary for completeness and request

missing information periodically and in a timely manner. Untoward events recorded in the diary will be reported as AEs according to the investigator's discretion and clinical judgment.

Subject entries in the diary will serve as source records. During study participation the investigator has access to the database holding the subject diary data. After study closure, the investigator will receive the diary records for their subjects, including audit trail records, in PDF format. The data will be transmitted to the eCRF by a validated transfer.

PROs will be administered at the start of prophylaxis treatment (baseline), every 6 months and at the end of study visit. Some questionnaires may not be administered in all participating countries due to the unavailability of linguistically validated translations for certain PRO measures in some countries. In addition, subjects who are younger than the minimal age limit required for these assessments will not complete the assessments.

10.5.2 Patient Reported Outcomes

The following PROs will be assessed at the start of prophylaxis treatment, every 6 months and at the end of study visit:

- Bleed and pain severity will be measured using the Haemo-SYM for subjects ≥ 18 years of age
- HRQoL will be assessed using the Short Form 36 (SF-36) for subjects ≥ 14 years of age
- HRQoL will be assessed using the Pediatric Quality of Life Inventory™ (PedsQL^{xiii}) for subjects < 14 years of age (for subjects aged ≥ 8 to < 14 years, the PedsQL Child report (23 items) will be completed; for subjects aged ≥ 5 to < 8 years, the PedsQL Parent report (23 items) will be completed; for subjects aged ≥ 2 and < 5 years, the PedsQL Parent report (21 items) will be completed; for subjects aged < 2 years, the PedsQL is not used)
- Patient satisfaction with treatment will be assessed using the Satisfaction Questionnaire (for subjects aged ≥ 12 years, the subject completes the questionnaire; for subjects aged < 12 years, the caregiver completes it on behalf of the subject)
- Patient Activity Level (for subjects aged ≥ 12 years, the subject completes the assessment; for subjects aged < 12 years, the caregiver completes it on behalf of the subject)

xiiiNOTE: Patients should be given the same questionnaire at follow-up that they were given at baseline, even if they move up an age range during the study.

Details on each of the PROs are as follows:

- **Haemo-SYM Questionnaire** – This is a self-administered, validated questionnaire designed to assess symptom severity in patients with hemophilia. This measure contains 17 items and includes 2 domains: Bleeds and Pain. Scores for each of these 2 domains can be calculated, with higher scores indicating more severe symptoms.
- **SF-36** – The SF-36 is a self-administered, validated questionnaire designed to measure generic HRQoL. This 36-item questionnaire measures 8 domains, including: Physical functioning, Role-physical, Bodily pain, General health, Vitality, Social functioning, Role emotional, and Mental health. Two summary scores can be calculated, the Physical Component Score, and the Mental Component Score. Additionally, scores can be calculated for each of the 8 domains. Higher scores indicate better health status.
- **PedsQL** – The PedsQL is a generic HRQoL instrument designed specifically for a pediatric population. Depending on the subject's age, the PedsQL contains 23 (for subjects aged ≥ 5 to < 14 years) or 21 (for subjects aged ≥ 2 to < 5 years) items and measures 7 domains: Physical Functioning, Emotional Functioning, School Functioning, Social Functioning, Psychosocial Summary, Physical Health, Total Score. Higher scores indicate better health status.
- **Patient Satisfaction Questionnaire** – This questionnaire is a non-validated measure that assesses the subject's (or via their caregiver) level of satisfaction with their treatment. For BAX 855 naïve subjects and BAX 855 naïve surgery subjects^{xiv}, at the end of study visit, the questionnaire also assesses the subject's preference between his previous treatment prior to the study and BAX 855. This questionnaire will be administered to all age groups.
- **Patient Activity Level** – Subjects will also be asked to estimate their activity levels. This will consist of a few questions asking subjects (or their caregiver) to rate their current level of activity. These data will be collected for all age groups.

xiv ie, subjects transitioning from the surgery study (Study 261204) into this continuation study that were naïve to BAX 855 prior to entry into the surgery study.

In addition, the following will be collected where applicable, for each occurrence:

- **Health Resource Use** – The subject (or their caregiver) will record the following events: (1) days missed from work/school (as appropriate) and days not able to perform normal activities outside of work/school due to hemophilia, (2) physician office visits, (3) hemophilia treatment site visits, (4) emergency room visits (reason and number), and (5) hospitalizations (reason, dates of hospitalization and associated length of stay). These data will be collected for all age groups.

10.6 Subject Completion/Discontinuation

A subject is considered to have completed the study when he/she ceases active participation in the study because the subject has, or is presumed to have, completed all study procedures according with the protocol (with or without protocol deviations).

Reasons for completion/discontinuation will be reported on the Completion/Discontinuation eCRF, including: completed, screen failure, AE (eg, death), discontinuation by subject (eg, lost to follow-up [defined as 3 documented unsuccessful attempts to contact the subject], dropout), physician decision (eg, pregnancy, progressive disease, non-compliance with IP/protocol violation(s)), study terminated by sponsor, or other (reason to be specified by the investigator, eg, technical problems). Regardless of the reason, all data available for the subject up to the time of completion/discontinuation should be recorded in the appropriate eCRF.

Every effort will be made to have discontinued subjects complete the study completion/termination visit. If the completion/termination visit is done as an additional, unscheduled visit, the assessment results shall be recorded with the completion/termination visit. If a subject terminates participation in the study and does not return for the completion/termination visit, their last recorded assessments shall remain recorded with their last visit. The reason for discontinuation will be recorded, and the data collected up to the time of discontinuation will be used in the analysis and included in the clinical study report. If additional assessments are required, the assessments shall be recorded separately. Assessments to be performed at the termination visit (including in cases of withdraw or discontinuation) can be found in Supplement 20.3 Schedule of Study Procedures and Assessments and Supplement 20.4 Clinical Laboratory Assessments.

In the event of subject discontinuation due to an AE, clinical and/or laboratory investigations that are beyond the scope of the required study observations/assessments may be performed as part of the evaluation of the event. These investigations will take

place under the direction of the investigator in consultation with the sponsor, and the details of the outcome may be reported to the appropriate regulatory authorities by the sponsor.

10.7 Procedures for Monitoring Subject Compliance

Subject compliance with the prescribed BAX 855 prophylaxis regimen will be monitored by review of subject diaries as described in Section 10.5.1. Other study procedures will be performed under the direct supervision of the investigator/a licensed healthcare professional at the study site, and thus, no other procedures for monitoring will be employed.

11. ASSESSMENT OF EFFICACY

11.1 Annualized Bleed Rate (ABR)

The primary measure of efficacy is the ABR. The ABR will be assessed based upon each individual bleeding episode, spontaneous or traumatic, recorded in the subject's diary, and/or recorded in the physician/nurse/clinic notes. A bleeding episode is defined as subjective (eg, pain consistent with a joint bleed) or objective evidence of bleeding which may or may not require treatment with FVIII. Bleeding episodes occurring at the same anatomical location (eg, right knee) with the same etiology (eg, spontaneous vs. injury) within 24 hours (± 2 hours) of onset of the first episode will be considered a single bleeding episode. Bleeding occurring at multiple locations related to the same injury (eg, knee and ankle bleeds following a fall) will be counted as a single bleeding episode.

11.2 Overall Hemostatic Efficacy Rating of BAX 855 for the Treatment of Bleeding Episodes

The subject or their caregiver will rate the severity (minor, moderate, or major) of the bleeding episode and will rate the overall treatment response at 24 (± 2) hours after the initiation of treatment using a 4-point efficacy rating scale (Table 4). Efficacy will not be assessed if any other FVIII concentrate is administered for the treatment of bleeding episodes. Since the efficacy rating is based to a large degree on cessation of pain, the investigator/subject shall, in particular in case of injury-related bleeding into one or more than one location, consider the injury-related symptoms when performing the efficacy rating 24 hours after initiating treatment and at resolution of bleed.

As per Table 4, multiple infusions of BAX 855 may be administered for the treatment of a bleeding episode. The overall response to all infusions combined is the rating that will be recorded.

Table 4 Efficacy Rating Scale for Treatment of Bleeding Episodes at 24 ± 2 Hours from the Initiation of Treatment and at Resolution of Bleed	
Excellent	Full relief of pain and cessation of objective signs of bleeding (eg, swelling, tenderness, and decreased range of motion in the case of musculoskeletal hemorrhage) after a single infusion. No additional infusion is required for the control of bleeding. Administration of further infusions to maintain hemostasis would not affect this scoring.
Good	Definite pain relief and/or improvement in signs of bleeding after a single infusion. Possibly requires more than 1 infusion for complete resolution.
Fair	Slight relief of pain and slight improvement in signs of bleeding after a single infusion. Required more than 1 infusion for complete resolution.
None	No improvement or condition worsens.

Details pertaining to all treatments for each bleed, including response to treatment, will be recorded by study subjects/subjects' caregiver in subject diaries provided by the sponsor or sponsor's representative. At each study visit, the investigator will review together with the subject/subject's caregiver the response to treatment and evaluate the hemostatic efficacy rating. It may become necessary to re-discuss the rating with the subject/subject's caregiver to ensure the Rating Scale is fully understood:

- Any inconsistency between the efficacy rating and the number of infusions used to treat a bleeding episode, or a response to treatment rated as "none" must be immediately clarified.
- If 2 or more responses to treatment of unique bleeding episodes are rated "fair", the investigator may re-evaluate the dosing regimen and the time from bleeding onset to the start of treatment. If a bleeding episode requires only one infusion but response to treatment is rated "fair", the rating should be evaluated and the Rating Scale should be reviewed with the subject/subject's caregiver.
- If more than one infusion was given to treat a bleeding episode, and the treatment was rated "excellent", additional information should be provided about the severity of the bleeding episode (see [Table 3](#)) and/or whether additional infusions were given to maintain hemostasis. If infusions were given to maintain hemostasis after resolution of bleed, this should be recorded accordingly in the eCRF.

11.3 Number of BAX 855 Infusions Needed for the Treatment of Bleeding Episodes

The number of BAX 855 infusions to treat each bleeding episode is determined by the subject, the subject's caregiver, and/or investigator, and is based upon the subject's response to treatment. An infusion is defined as completion of administration of the calculated dose of BAX 855. If an infusion is interrupted, eg, due to vascular access issues, and must be re-started, it will be recorded as 1 infusion. If an infusion is terminated for any reason prior to completion of infusion and not restarted, it will be recorded as an infusion; reasons for interruption of the infusion will be recorded.

11.4 Time Intervals Between Bleeding Episodes

The time interval between bleeding episodes will be calculated based upon the date and time reported for each bleeding episode. The subject, the subject's caregiver, and/or investigator will determine when a bleeding episode has occurred (see Section 11.1 above).

11.5 Weight-Adjusted Consumption of BAX 855

Weight-adjusted consumption of BAX 855 will be determined based upon the amount of BAX 855 infused, as record in subject's diary and the subject's weight, as measured at the study site.

12. ASSESSMENT OF SAFETY

12.1 Adverse Events

12.1.1 Definitions

An AE is defined as any untoward medical occurrence in a subject administered an IP that does not necessarily have a causal relationship with the treatment. An AE can therefore be any unfavorable and unintended sign (eg, an abnormal laboratory finding), symptom (eg, rash, pain, discomfort, fever, dizziness, etc.), disease (eg, peritonitis, bacteremia, etc.), or outcome of death temporally associated with the use of an IP, whether or not considered causally related to the IP.

12.1.1.1 Serious Adverse Event

A **serious** adverse event (SAE) is defined as an untoward medical occurrence that at any dose meets one or more of the following criteria:

- Outcome is fatal/results in death (including fetal death)
- Is life-threatening – defined as an event in which the subject was, in the judgment of the investigator, at risk of death at the time of the event; it does not refer to an event that hypothetically might have caused death had it been more severe.

- Requires inpatient hospitalization or results in prolongation of an existing hospitalization – inpatient hospitalization refers to any inpatient admission, regardless of length of stay.
- Results in persistent or significant disability/incapacity (ie, a substantial disruption of a person’s ability to conduct normal life functions)
- Is a congenital anomaly/birth defect
- Is a medically important event – a medical event that may not be immediately life-threatening or result in death or require hospitalization but may jeopardize the subject or may require medical or surgical intervention to prevent one of the other outcomes listed in the definitions above. Examples of such events are:
 - Intensive treatment in an emergency room or at home for allergic bronchospasm, blood dyscrasias, or convulsions that do not result in hospitalization, or development of drug dependence or drug abuse
 - Reviewed and confirmed seroconversion for human immunodeficiency virus (HIV), hepatitis A virus (HAV), hepatitis B virus (HBV), hepatitis C virus (HCV), hepatitis E virus (HEV), or parvovirus B19 (B19V). Seroconversion to HBV is only considered an SAE in the absence of vaccination; seroconversion of HBsAb from negative to positive will not be considered an SAE (or an AE)
 - Development of a confirmed inhibitor to FVIII with an inhibitor level ≥ 0.6 BU, as measured by the Nijmegen assay modification of the Bethesda assay
 - Severe hypersensitivity/allergic reactions to BAX 855

Uncomplicated pregnancies, following maternal exposure to IP are not considered an (S)AE; however, any pregnancy complication or pregnancy termination by therapeutic, elective, or spontaneous abortion shall be considered an SAE.

12.1.1.2 Non-Serious Adverse Event

A **non-serious** AE is an AE that does not meet the criteria of an SAE.

12.1.1.3 Unexpected Adverse Events

An unexpected adverse event is an AE whose nature, severity, specificity, or outcome is not consistent with the term, representation, or description used in the Reference Safety Information (eg, IB, package insert). “Unexpected” also refers to the AEs that are mentioned in the IB as occurring with a class of drugs or as anticipated from the pharmacological properties of the drug, but are not specifically mentioned as occurring with the particular drug under investigation.

For the purposes of this study, each unexpected AE experienced by a subject undergoing study-related procedures will be recorded on the AE eCRF.

12.1.1.4 Preexisting Diseases

For subjects transitioning into this continuation study from a prior BAX 855 study, any AEs that occurred during these other BAX 855 studies and which are still ongoing in this continuation study will be considered as “ongoing” and not as a preexisting disease.

AEs that were resolved in the previous BAX 855 studies will be documented as medical history for subjects who enter this continuation study. If a subject exited this continuation study to participate in the surgery study, upon return, any AEs that started and resolved during the surgery study will be documented as medical history.

Preexisting diseases that are present before entry in to the study are described in the medical history, and those that manifest with the same severity, frequency, or duration after IP exposure, will not be recorded as AEs. However, when there is an increase in the severity, duration, or frequency of a preexisting disease, the event must be described on the AE eCRF.

12.1.2 Assessment of Adverse Events

Each AE from the first IP exposure until study completion/discontinuation will be described on the AE eCRF using the medical diagnosis (preferred), or, if no diagnosis could be established at the time of reporting the AE, a symptom or sign, in standard medical terminology in order to avoid the use of vague, ambiguous, or colloquial expressions (see definition in Section 12.1). Each AE will be evaluated by the investigator for:

- Seriousness as defined in Section 12.1.1.1
- Severity as defined in Section 12.1.2.1
- Causal relationship to IP exposure or study procedure as defined in Section 12.1.2.2

For each AE, the outcome (ie, recovering/resolving, recovered/resolved, recovered/resolved with sequelae, not recovered/not resolved, fatal, unknown) and if applicable action taken (ie, dose increased, dose not changed, dose reduced, drug interrupted, drug withdrawn, not applicable, or unknown) will also be recorded on the AE eCRF. Recovering/resolving AEs will be followed until resolution, medically stabilized, or 30 days after the study completion/termination visit, whichever comes first). If the severity rating for an ongoing AE changes before the event resolves, the original AE

report will be revised (ie, the event will not be reported as separate AE). During the course of any AE, the highest severity rating will be reported.

Deviations from the protocol-specified dosage (including overdosing, underdosing, abuse, and withdrawal, treatment errors (including incorrect route of administration, use of an incorrect product, and deviations from the protocol-defined dosing schedule), failures of expected pharmacological actions, and unexpected therapeutic or clinical benefits will be followed with regard to occurrence of AEs, lack of efficacy, and/or other observations because these events may be reportable to regulatory authorities.

Any pregnancy that occurs after administration of IP will be reported on a Pregnancy Form and followed-up at 1 year post-delivery, if feasible.

If an investigator becomes aware of an SAE occurring in a subject after study completion, the SAE must be reported on the SAE Form within 24 hours after awareness; no additional reporting on eCRFs is necessary.

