12.8 Vital Signs

Vital signs will include body temperature ($^{\circ}\text{C}$ or $^{\circ}\text{F}$), respiratory rate (breaths/min), pulse rate (beats/min), and systolic and diastolic blood pressure (mmHg). Height (for subjects less than 18 years of age at the time of enrollment) (in or cm) and weight (lb or kg) will also be collected.

Vital signs will be measured at the screening visits, start of prophylaxis visit, follow-up visits, and end of study visit.

Blood pressure will be measured when subjects are in the supine position.

Vital sign values are to be recorded on the eCRF. For each abnormal vital sign value, the investigator will determine whether or not to report an AE (see definition in Section 12.1 and record the medical diagnosis (preferably), symptom, or sign on the AE eCRF). Additional tests and other evaluations required to establish the significance or etiology of an abnormal value, or to monitor the course of an AE should be obtained when clinically indicated. Any abnormal value that persists should be followed at the discretion of the investigator.

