20.2.1.4 End of Study Visit

The procedures listed here should also be performed if a subject withdraws or discontinues from the study. At least 84 to preferably 96 hours must have elapsed since the previous BAX 855 administration and the subject must not be actively bleeding.

The following assessments will be performed:

Pre-infusion:

- Physical examination, including height (for subjects aged < 18 years at enrollment) and body weight
- Pregnancy test if female of childbearing potential
- Collection of subject e-diary and review of entries and discussion with subject
 - Review bleeding episodes and their treatment
 - Adverse events
 - Concomitant medications and non-drug therapies
- PROs:
 - Bleed and pain severity using Haemo-SYM (≥ 18 years), HRQoL using SF-36 (≥ 14 years), HRQoL using PedsQL (< 14 years), patient satisfaction with treatment using the Satisfaction Questionnaire (all ages), and Patient Activity Level (all ages)
- Laboratory assessments within 30 minutes of start of infusion:
 - FVIII activity and antigen
 - TGA parameters (optional)

- VWF antigen(optional)
- Immunogenicity tests
- Hematology, clinical chemistry and lipid panel
- Vital signs (within 15 minutes of IP infusion)

Determination of IR

- Infusion of 60 ± 5 IU/kg BAX 855

Post-infusion:

At 30 ± 15 min post-infusion:

- FVIII activity and antigen
- TGA parameters (optional)
- Vital signs

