20.2.2.6 End of Study Visit

The procedures listed here should also be performed if a subject withdraws or discontinues from the study. At least 84 to preferably 96 hours must have elapsed since the previous BAX 855 administration and the subject must not be actively bleeding.

The following assessments will be performed:

Pre-infusion:

- Physical examination, including height (for subjects aged < 18 years at enrollment) and body weight
- Collection of subject e-diary and review of entries and discussion with subject
 - Review bleeding episodes and their treatment
 - Adverse events
 - Concomitant medications and non-drug therapies
- PROs:
 - Bleed and pain severity using Haemo-SYM (≥ 18 years), HRQoL using SF-36 (≥ 14 years), HRQoL using PedsQL (< 14 years), patient satisfaction with treatment using the Satisfaction Questionnaire (all ages), and Patient Activity Level (all ages)
- Laboratory assessments within 30 minutes of start of infusion:
 - FVIII activity and antigen assays
 - TGA parameters and VWF antigen (optional in subjects aged < 12 years)
 - Immunogenicity tests
 - Hematology, clinical chemistry and lipid panel
- Vital signs (within 15 minutes of IP infusion)

Determination of IR:

- Infusion of 60 ± 5 IU/kg BAX 855

Post-infusion:

At 30 ± 15 min post-infusion:

- FVIII activity and antigen
- TGA parameters (optional in subjects aged < 12 years)
- Vital signs

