- An AE is considered severe if the eCRF question "Severity" is answered "Severe".
- An AE is considered related as assessed by the Investigator if the AE is indicated as "Possibly related" or "Probably related" in the eCRF. An AE is considered unrelated as assessed by the Investigator if the AE is indicated as "Not related" or "Unlikely related" in the eCRF.
- An AE is considered related as assessed by the Sponsor if the Sponsor Medic deem the AE related to the study medication. Prior to any analyses described in this SAP, a list of all AEs in the database is to be provided to the Sponsor Medic to assess relationship from a Sponsor perspective of AE to study medication.
- An AE is considered leading to discontinuation of study medication if indicated as "Drug withdrawn" in the eCRF.
- An AE is considered leading to discontinuation of study if the AE is indicated as the primary reason why the subject did not complete the study from the *Study Completion/Termination* eCRF panel.
- An AE is considered as leading to death if the question "Did the serious event result in death" is indicated as "Yes" or if the outcome in the eCRF is indicated as "Fatal".
- An AE is considered to be an allergic reaction if the question "Was this event considered to be an allergic reaction" is indicated as "Yes".
- An AE is considered to be a thrombotic event if the question "Is this a thrombotic event" is indicated as "Yes" in the eCRF.

AEs that occurred during or after BAX 855 are to be presented for the SAS. Summary tables are to indicate the number of subjects who experienced AEs as well as the number of AEs. Summaries for BAX 855 as indicated in the latest version of the Output Templates are also to include the rate of AEs per 100 infusions and rate of AEs per year. In addition, tables are to be prepared to summarize each AE by system organ class and preferred term, the number of subjects who experienced an AE at least once, the rate of subjects with AE(s), AEs per 100 infusions and AE rate per year. AE summaries by seriousness, severity and relationship are to be presented as well.

AE rate per 100 infusions is to be determined as the number of AEs divided by the total number of infusions (regardless of the reason the infusion was administered) in the study multiplied by 100.

AE rate per year is to be determined as the number of AEs divided by the OPE in years in the current study across all subjects.

All AEs for each subject, are to be listed for the SAS.

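### No collection of new adverse events is planned beyond about 15 to 45 minutes after the end-of-study infusion, so delayed reactions to the last dose can be missed

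*Protocol*

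**What the plan says.** **Recording window.** Protocol 12.1.2: "Each AE from the first IP exposure until study completion/discontinuation will be described on the AE eCRF". Protocol 10.6 treats a subject as complete once he or she has, or is presumed to have, "completed all study procedures according with the protocol".

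**End-of-study visit.** Protocol 20.2.1.4 (fixed dose) and 20.2.2.6 (PK-tailored) use the same order, and both apply to subjects who withdraw or discontinue:

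- Among the pre-infusion items: "Collection of subject e-diary and review of entries and discussion with subject", with adverse events as a sub-item.
- Then, to determine recovery: "Infusion of 60 ± 5 IU/kg BAX 855".
- Then, "At 30 ± 15 min post-infusion": FVIII activity and antigen, TGA parameters (optional for some subjects) and vital signs. Nothing later is scheduled.

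**After completion.** The 30-day period in 12.1.2 applies to AEs that are already recovering or resolving. An SAE that the investigator learns of after completion must be reported on the SAE form within 24 hours, but "no additional reporting on eCRFs is necessary".

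**Analysis.** SAP 8.1 takes AEs from the Adverse Events eCRF panels. For the rate per 100 infusions it divides the number of AEs by the "total number of infusions (regardless of the reason the infusion was administered) in the study multiplied by 100". For the rate per year it divides by the observation period for efficacy (OPE), which SAP 6.7 ends at the last BAX 855 infusion.

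**The concern.** At every other visit the AE review also comes before the infusion, but there it does no harm: the subject keeps the diary, which records untoward events (Protocol 10.5.1), and the next visit reviews it. After the end-of-study infusion both safeguards are gone. A non-serious reaction that starts hours or days later has no planned route into the database. A serious one reaches the sponsor only if the investigator hears of it, and even then need not appear in the AE tables.

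The plan itself treats late onset as relevant. SAP 8.1 separates AEs during treatment, within 24 hours after it and more than 24 hours after it, and Protocol 6.5 names hypersensitivity through anti-PEG antibodies as a possible risk. AE occurrence is a secondary safety outcome, and Protocol 16.4 provides no data monitoring committee. There is also a smaller issue of rates: an infusion with almost no follow-up may be counted in the denominator on the same footing as all the others.

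**Working it through.** The plan gives no figure on this point to reproduce. The check sets out which events can be captured after the last infusion, then bounds the effect on the two AE rates.

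**1. Routes for an event after the end-of-study infusion**

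- *Onset within about 15 to 45 minutes:* capturable. Vital signs are taken at 30 ± 15 minutes, and under Protocol 12.8 "For each abnormal vital sign value, the investigator will determine whether or not to report an AE". Completion follows the last procedure, so the 12.1.2 window is still open.
- *Later, non-serious:* the diary has been handed in, no contact is planned, and the 30-day rule covers existing events only. No planned route.
- *Later, serious:* SAE form if the investigator becomes aware; eCRF entry not required; SAP tables draw on the eCRF. It need not be tabulated.

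**2. Infusions per subject**

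Inputs: twice-weekly dosing (Protocol 8.7.3.1), participation of about 3 to 12 months (Protocol 8.3), about 250 enrolled (Protocol 13.1). Assumed: one end-of-study infusion per subject and no other infusions beyond twice weekly.

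n = months/12 × 52 × 2, giving n = 26 at 3 months and n = 104 at 12 months.

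Consistency check: 100 EDs ÷ 2 per week = 50 weeks = 11.5 months, in line with the stated upper duration of about 12 months.

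**3. Rate per 100 infusions**

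The last infusion is 1/n of the denominator; removing it multiplies the rate by n/(n − 1).

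- 3 months: 1/26 = 3.8%; 26/25 = 1.040.
- 12 months: 1/104 = 1.0%; 104/103 = 1.0097.

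An illustrative (assumed) rate of 5.00 per 100 becomes 5.20 or 5.05. If all 250 attended, this would be 250 infusions out of 250 × 26 = 6,500 to 250 × 104 = 26,000. These are upper bounds: reactions within 15 to 45 minutes can be caught, and bleed treatment, more frequent PK-tailored dosing and extension beyond 100 EDs all raise n. An assumed 24 months gives n = 208, or 0.5%.

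**4. Rate per year**

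OPE stops on the day of the last infusion, so at most one weakly observed day is counted: 1/91.3 = 1.1% at 3 months and 1/365.2425 = 0.3% at 12 months.

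**5. Is the recovery infusion in the denominator?**

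SAP 4.2 lists a separate eCRF panel for incremental recovery infusions. SAP 6.7 and 8.1 name only the Study Infusions panels as their infusion source. The 8.1 denominator, which disregards purpose, points to inclusion; the listed source points the other way. The SAP does not settle it.

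**6. What an added AE window would do to the rates**

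Assume a constant AE rate over time. Adding 30 days of events with no change to infusions or OPE inflates the rates by 30/91.3 = 33% at 3 months and 30/365.2 = 8% at 12 months, more than the 1% to 4% in step 3. A window of one usual between-infusion interval (3 or 4 days under the fixed regimen) gives the last infusion the same follow-up as the others, so the per-infusion rate is then matched. The yearly rate would still rise by up to 4/91.3 = 4.4% or 4/365.2 = 1.1% unless the same days are added to its denominator.

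**The case against.** A reader might infer that the last infusion has no AE follow-up at all and that this definitely depresses the AE rates. The documents do not support that. Vital signs after the infusion can lead to an AE report. The footnotes to the schedules in Protocol 20.3 have AEs reviewed continuously and assessed at the end-of-study visit, without limiting this to the time before the infusion. Later SAEs known to the investigator still go to the sponsor. Of the two rates, the yearly one barely moves, and whether the other counts recovery infusions is open.

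It can also be said that the recovery infusion is not a new exposure. The same infusion is given at earlier visits, followed by weeks of diary and visit capture, and prophylactic doses may themselves go up to 80 IU/kg. For most subjects the gap is one repeat of an exposure already observed, around or after 100 EDs. Ending routine collection at completion is a design choice, and a move to another FVIII product would complicate attribution. Finally, a 30-day window added without thought would distort the rates more than the present gap does.

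These points stand, and they limit the size of the problem. They do not supply a route for a delayed reaction to the last infusion, which is what remains.

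**Conclusion.** The gap is real but narrow. For anyone who attends the end-of-study visit, whether completing or leaving early, no collection of new AEs is planned beyond about 15 to 45 minutes after the last infusion, and a later SAE can reach the sponsor without reaching the SAP tables. Missed delayed events are the main reason to act.

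The rate bias is secondary: at most about 4% at 3 months and 1% at 12 months, downward, for the rate per 100 infusions only. It rests on twice-weekly dosing, no capture of reactions after the last infusion, and recovery infusions being counted. The rate is descriptive, with no test or threshold attached. This is a cheap improvement to safety capture; it does not show that the AE results would be materially wrong.

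**What to change.** **Protocol 12.1.2.** Extend eCRF recording of new AEs and SAEs to a stated short interval after the last BAX 855 infusion, for example one usual between-infusion interval. Add one documented telephone contact at its end and a flag for any other FVIII product started in the meantime.

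**SAP 8.1.** Keep numerator and denominator matched. With the short interval, add the same days to the time at risk for the yearly AE rate only, leaving OPE unchanged for bleeding rates. If a longer window such as 30 days is preferred, tabulate those post-treatment AEs separately and leave them out of both rates. Dropping the end-of-study infusion from the denominator is a weaker substitute: it recovers no missed events and would leave that infusion's early reactions in the numerator.

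**SAP 6.7 and 8.1.** State whether infusions on the incremental recovery panel count in the per-100-infusion denominator.

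**Cost.** One telephone contact per subject, a product flag, and wording in both documents. Dosing and visit procedures are unchanged.
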